### **5.6 Post-Procedure Care**

Standardization of medical management will occur according to the following:

- General medical management according to AHA guidelines
- Admission to monitored or intensive care unit for at least 24 hours
- Close monitoring of BP with treatment according to AHA guidelines
- Follow-up imaging studies as indicated in any patient with neurologic deterioration

A post-procedural CT scan will be obtained within 24 hours in all patients undergoing Apollo / Artemis MIES. Neurological and functional exams will be conducted within 24 hours (+/- 12 hours) in patients undergoing Apollo / Artemis MIES. A CT (preferred) or MR scan will also be obtained 7 days after enrollment. Additional imaging will be obtained at the discretion of the managing service based upon clinical data and established institutional standard of care.

## **5.7 Recovery**

The subject will be recovered from the procedure and discharged from the hospital as per standard practices.

### **5.7.1 Discharge**

At discharge, the following will be completed by a qualified member of the research or clinical care team: a focused physical exam, a neurological exam (including GCS, NIHSS and mRS), a review of any adverse events, and a review of selected current medications. If discharge occurs before 7 days after enrollment, the discharge clinical examinations will also substitute for the 7-day clinical evaluation and a standard of care CT (preferred) or MR will be obtained at that time.

## **5.8 Hospital Costs**

For each subject, overall costs will attempt to be collected for the initial hospitalization during which study enrollment took place. These costs will include device costs (the market price for each device), materials used to treat the hemorrhage, and number of days spent in the hospital (ICU and non-ICU length of stay). In summary, the total amount billed and the total amount reimbursed will be collected and assessed, if possible.

## **5.9 Follow-Up Examination**

### **5.9.1 Clinical**

Several clinical outcome measures were selected for this study. These were chosen on the basis of their reliability, familiarity to the neurologic community, adaptability for use in patients who have had a stroke, and comparability to end points used in other trials of intracranial hemorrhage. All scores will be recorded in electronic case report forms as well as within the medical record and/or in research source documentation as appropriate.

1. Modified Rankin Scale: mRS is an overall assessment of global handicap. In the original Rankin Scale, a score of zero indicates the absence of symptoms and a score of 5, severe disability. The modified Rankin Scale adds a score of 6 for fatal outcomes. A historical mRS will be obtained to assess the patient's level of function prior to the ICH. The score will be repeated as specified in Table 1.

2. Barthel Index: The Barthel Index is an ordinal scale used to measure performance of activities of daily living. A historical Barthel Index score will be obtained to assess the patient's level of function prior to the ICH. The score will be repeated as specified in Table 1.
3. The National Institutes of Health Stroke Scale is a 42-point scale that quantifies neurologic deficits in 11 categories. Normal function without neurologic deficit is given a score of zero. NIHSS should be done by a certified examiner as close to the specified times as possible.
4. EQ-5D-5L is a standardized instrument for use as a measure of health outcome. Applicable to a wide range of health conditions and treatments, the questionnaire provides a simple descriptive profile and a single index value for health status.
5. Stroke Impact Scale: Additionally a quality of life scale outcome measure will be utilized in this study. Quality of life scales are designed to be sensitive to changes in outcome from mild and moderate stroke undetected by other outcome measures. Important parameters not fully interrogated by conventional outcome scales can be assessed by quality of life scales, including emotion, communication, cognition, and social role function. Standard measures, such as the mRS, primarily evaluate physical aspects of stroke outcome, not addressing more relevant quality of life measures. The Stroke Impact Scale is a validated assessment of quality of life specifically in patients with stroke.  
45 45 4547

All day 7, discharge, day 90, day 180 and day 360 clinical outcome measures will be assessed by a qualified member of the research or clinical team. The schedule of neurological assessments is listed in Table 1. At each visit, the patient medical record will be surveyed for any new or interim neurological adverse or serious adverse events. In addition, the patient or LAR will be asked about any interim neurological adverse or serious adverse events. The subject or LAR will also be specifically asked about any interim neurosurgical procedures.

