### ***Secondary Endpoints:***

- Stroke Impact Scale – Mobility at 180 days
- Stroke Impact Scale – ADLs at 180 days
- EQ-5D-5L at 180 days
- Length of hospital stay
- Clinical Efficacy Endpoint: 180-day global disability assessed via the modified Rankin score (mRS), categorized as either mRS  $\leq 3$  or mRS  $> 3$
- Technical Efficacy Endpoint: Rate of surgical success
  - Predominantly or Only ICH: Reduction to  $< 15$  cc total volume AND  $>60\%$  reduction in hemorrhage volume on immediate post-treatment CT scan
  - Predominantly or Only IVH: mGraeb score of  $\leq 5$  on day 7 CT scan
- Safety Endpoint: Rate of mortality at 90 days

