#### **4.6 Screening and Baseline Evaluation**

During screening and baseline evaluations consent is obtained, medical history screened, available clinical/neurological exams obtained, and laboratory work and imaging information per institutional standard of care are evaluated to determine patient eligibility. The baseline neurologic examination will be performed by a health care provider or study team member, certified to administer the exams and able to give an unbiased neurological and functional assessments (NIHSS, Glasgow Coma Score (GCS), and perform a historical mRS determination). CT imaging must be performed to provide an initial diagnosis of IPH (intraparenchymal hemorrhage). Hemorrhage volume will be determined using the A x B x C/2 method. Subsequent stability imaging (CT (preferred) or MR) must be obtained at least 6 hours after the presenting scan to confirm stability in the hemorrhage volume. A CTA (or MRA for CTA ineligible patients) must also be performed, as standard of care; either at presentation with the diagnostic CT or with the stability scan. Enrollment will occur in consented patients with a stable hemorrhage volume on follow up CT or MR (< 5 cc increase in volume). In the case that the stability scan demonstrates hemorrhage volume increase > 5 cc, a second stability scan can be obtained q12 hours until either stability is demonstrated or the patient is outside of the window for treatment (72 hours from the time of ictus). In the case of a “spot sign”, follow up CTA (or MRA if ineligible for CTA) can be obtained q12 hours to show resolution of the “spot sign” prior to enrollment. An NIHSS must be obtained prior to enrollment, and the score must be  $\geq 6$  for inclusion in the study. A pregnancy test will be conducted for applicable subjects (<50 years old and of child bearing potential). Once the patient meets all eligibility criteria, has undergone a stability scan, and the patient or LAR (legally authorized representative) has provided written informed consent, they will be considered enrolled in the study. Enrolled patients will be treated using Apollo / Artemis MEIS

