## 7.6 *Blinding*

This study is not blinded. Blinding is difficult, if not impossible, from a clinical perspective. It is not possible to blind the Investigator who treats the patient, the clinical staff or the research team. Additionally, physicians treating subjects who experience an adverse event after must know how the hemorrhage was treated in order to effectively report the adverse event and plan further treatment. Blinding the study is not required for interpretation of study outcomes.

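### The certified, unbiased rater standard set for the baseline exam is not carried to the 180-day mRS, and nothing keeps the operator from scoring it

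*Combined protocol and SAP*

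**What the plan says.** Section 4.6 covers the baseline NIHSS, GCS and historical mRS. The examination is "performed by a health care provider or study team member", and that person must be "certified to administer the exams and able to give an unbiased neurological and functional assessments".

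Section 5.9.1 covers day 7, discharge and days 90, 180 and 360. There the "clinical outcome measures will be assessed by a qualified member of the research or clinical team". Section 5.7.1 uses nearly the same words at discharge, for an exam that includes the mRS: "the following will be completed by a qualified member of the research or clinical care team". Item 3 of Section 5.9.1 adds that "NIHSS should be done by a certified examiner as close to the specified times as possible". The mRS item has no matching sentence.

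Section 7.6 states that the study is unblinded: "It is not possible to blind the Investigator who treats the patient, the clinical staff or the research team". It ends with "Blinding the study is not required for interpretation of study outcomes".

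The 180-day mRS, split at 3 or below versus above 3, is listed as the clinical efficacy endpoint among the secondary endpoints (synopsis and Section 3.2). Section 7.2 reports it as a proportion with an exact two-sided 95% interval.

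**The concern.** The protocol states its stricter rater standard for the entry examination and a looser one for the visits that produce the outcome. The word qualified is not defined where it is used. The 3-versus-4 boundary calls for judgment, and the person who did the surgery has an interest in the answer. A rater can know the treatment and still not be the operator, so the impossibility of blinding does not settle who should score.

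The other judged outcomes are protected better. A core-lab neuroradiologist reads the scheduled scans (Section 5.9.2). The specified adverse events go to a medical monitor and to the DSMB acting as events committee (Section 5.9.3). The mRS gets no comparable review. At stake is how far the reported mRS 0-3 proportion can be trusted when it is the only arm's result.

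**Working it through.** **Step 1. Rater rules compared.**

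- Baseline NIHSS, GCS, historical mRS (4.6): certified and unbiased. Any provider or study team member may serve; the operator is not excluded.
- Follow-up NIHSS (5.9.1, item 3): certified examiner.
- Follow-up mRS (5.9.1; discharge in 5.7.1): qualified member of the research or clinical team. Certification, lack of bias and separation from the operator are not mentioned.

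The textual gap is therefore the certified/unbiased standard. Separation from the operator is absent at both time points.

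**Step 2. Search for a rule elsewhere.** Section 12 requires personnel to be suitably trained and experienced for their tasks. Section 13 recommends a study coordinator. Section 14 requires a delegation log. Section 21 has key outcome data checked against source. None of these says who may score the mRS. The Manual of Procedures is not in the file, and the protocol does not refer to it for mRS rating.

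**Step 3. Which endpoints are exposed.** The primary endpoints are recruitment and whether a 180-day mRS was obtained (synopsis, Sections 6 and 7.1); neither depends on the value scored. Mortality needs no rating. The exposed results are the 180-day mRS 0-3 proportion and the ordinal mRS model in Section 7.4. The mRS is collected at 90 days (Table 1), but no 90-day mRS endpoint is defined.

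**Step 4. Scale.** The plan gives no expected mRS 0-3 rate and no rater-error figure, and n (up to 50, Section 7.1) comes without a calculation, so there is no stated figure to reproduce. One reclassified patient moves the proportion by 1/50 = 2 percentage points.

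For illustration, assume that 20 of 50 patients are truly mRS 0-3. This 40% and the shifts below are assumptions, not figures from the documents. The exact interval for x of n runs from the 2.5% quantile of Beta(x, n−x+1) to the 97.5% quantile of Beta(x+1, n−x):

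- 20/50 = 40%: 26.4% to 54.8%
- 1 patient scored up, 21/50 = 42%: 28.2% to 56.8%
- 2 scored up, 22/50 = 44%: 30.0% to 58.7%
- 5 scored up, 25/50 = 50%: 35.5% to 64.5%
- 5 scored down, 15/50 = 30%: 17.9% to 44.6%

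**Step 5. What the interval leaves out.** Suppose the chance of a scored mRS 0-3 is 0.40 + b while the true rate is 0.40. Coverage is the sum of Binomial(50, 0.40 + b) probabilities over all x whose interval contains 0.40:

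- b = 0: 97.1%
- b = 0.04: 93.8%
- b = 0.10: 76.0%

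The interval describes sampling error only. It gives no sign of a systematic rater shift.

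**The case against.** The strongest reply is that this is a feasibility study. The primary question is whether patients can be recruited and their 180-day mRS captured. The mRS 0-3 rate is one of several secondary results, and no threshold or go/no-go rule depends on it. That stands, and it limits the weight of the point.

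The site safeguards also count for something. Training requirements, the delegation log and source checks give traceability, and the Barthel Index and Stroke Impact Scale at the same visits offer a rough cross-check. None of them sets a standard for the mRS rater.

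A strict bar on operator scoring could lose a 180-day score when no one else is present, at 1/50 = 2 points of the primary capture rate each time. That is a fair objection to a strict bar, and a fallback rule meets it. A coordinator is only recommended and works under the site investigator, so using one gives separation from the procedure but not full independence.

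A reader might infer more than the text supports:

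- *That operators will do the scoring.* No section names the operator as rater; it is permitted by silence.
- *That the rate will drift upward.* Leniency is plausible, but the documents show neither its direction nor its size.
- *That Section 7.6 defends operator rating.* It discusses who can be blinded, not who rates. Its closing sentence is merely too broad.
- *That Section 4.6 already bars the operator.* It does not.
- *That the rate is meant to be read against outside rates.* The Conclusions in Section 1.1 say only that a single-arm study should precede a randomized trial.

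**Conclusion.** The gap is real and worth closing. The protocol asks for a certified, unbiased examiner at baseline, asks less at follow-up, keeps certification for the NIHSS only, and leaves the operator free to score the 180-day mRS. With one arm, any rater leniency passes straight into the mRS 0-3 proportion and is not reflected in its interval.

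The only size that follows from the documents is 2 percentage points per reclassified patient with 50 scored. The 40% base rate, the shifts and the coverage figures are illustrations of scale, not estimates of bias. The conclusion assumes that no document outside the file sets an mRS rater rule. It concerns a secondary endpoint and the related mRS analysis, and leaves the primary endpoints and mortality untouched.

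**What to change.** 1. In Section 5.9.1, require the 180-day mRS, and preferably the other follow-up mRS scores, to be given by someone who meets the certified and unbiased standard of Section 4.6.
2. As a safeguard that goes beyond Section 4.6, have it scored by an existing site team member who did not perform the procedure, for example the study coordinator where there is one.
3. Add a fallback: if no such person is available at the visit, whoever is available scores the mRS, so that capture is not lost.
4. Record the rater's role on the CRF. Report how many 180-day scores came from anyone involved in the procedure, and show the mRS 0-3 proportion with and without them. This comparison is descriptive, since the patients scored by operators may differ from the rest.
5. Limit the last sentence of Section 7.6 to treatment allocation.

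The cost is mRS certification for staff already at the sites, one CRF field and a few sentences of text. No central assessor or extra visit is needed. The change is best made before 180-day scores accrue, because the rater's role is hard to reconstruct reliably afterwards.

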### 5.9.2 *Cross-Sectional Imaging*

All scheduled CT and MR studies will be assessed by a central core lab neuroradiologist. The volume of hemorrhage on the diagnostic scan will be calculated using a standard  $A \times B \times C/2$  calculation. On the CT slice with the largest area of ICH, the largest diameter (A) is measured in cm. The dimension of the hemorrhage perpendicular to the largest diameter (B), represents the second diameter. The third diameter (C) will be calculated either by multiplying the number of CT slices which depict the hematoma by the slice thickness or determined on coronal or sagittal reconstructions.

Hemorrhage volumes will also be assessed using a manual volume measurement technique on the diagnostic scan and all subsequent scans, as defined in the Imaging Manual. Intraventricular hemorrhage will be assessed on each scan and graded according to a modified Graeb score (see the Imaging Manual and Manual of Procedures).

Scheduled imaging studies include the diagnostic/admission scan, the stability scan(s) (at least 6 hours after the diagnostic scan), CT or MR angiogram (with either the diagnostic or stability scan), Post-operative post-presentation scan 7 day post presentation scan.

Table 1. Schedule of Events

ACTIVITY	SCREENING /BASELINE	STABILITY SCAN (at least 6 hours post initial CT)	TREATMENT	24 hour post - MIES (+/-12)	DISCHARGE AND/OR 7 DAYS (+/- 1 day)	3 MONTHS (+/- 14 days)	6 MONTHS (+/- 21 days)	1 YEAR or END OF STUDY (+/- 35 days)
Informed Consent	X							
Inclusion/ Exclusion Criteria	X							
Medical History	X							
Focused Exam	X	X		X	X	X	X	X
Standard of Care Labs	X	X		X	X			
Standard of Care CT/MR	X	X	X		X			
CTA or MRA	X (or at stability)	X (if not done with Baseline)						
Barthel	Historic					X	X	X
NIHSS	X	X		X	X	X	X	X
GCS	X	X		X	X	X	X	X
mRS	Historic			X	X	X	X	X
Stroke Impact Scale (QOL)						X	X	X
ED-5D-5L						X	X	X
Pregnancy Test if childbearing potential	X	Or X						
Con Medications	X	X	X	X	X	X	X	X
Apollo / Artemis MIES under general anesthesia within 24 hours of sx onset			X					
Adverse Events			X	X	X	X	X	X
All brain imaging sent to central core lab	within 48 hours of test	within 48 hours of test	within 48 hours of test	within 48 hours of test	within 48 hours of test			

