### 5.9.3 *Serious Adverse Events*

All serious adverse events occurring during the 365 days of study participation will be recorded. Adverse events and serious adverse events are critical endpoints and will be assessed as they occur and at the scheduled clinic visits. A serious adverse event is one that is fatal or life-threatening, is permanently or substantially disabling, requires or prolongs hospitalization, or any event that the treating clinician judges to be a significant hazard. For each recorded serious adverse event, the patient's attending physician will be asked to classify the causal relationship of the event to the study treatment as probable, possible, unlikely, and unrelated. Detailed form and narrative reports of the following specific adverse events will be obtained:

- Death (all cause) within 90 days of enrollment
- Death within 7 days of enrollment: Immediate periprocedural death
- Symptomatic Re-Hemorrhage or New Hemorrhagic Event: any new intracranial hemorrhage or increase in size of pre-existing hemorrhage (IPH, IVH or extra-axial bleed) within 90 days associated with an increase of 4 or more points on the NIHSS or GCS increase  $\geq 2$  persisting for at least 24 hours and/or requiring emergency surgical decompression or resulting in death.
- Symptomatic Evolution of Perihematomal Edema: Edema with increased mass effect or uncontrolled ICPs within 90 days requiring emergency surgical decompression NOT related to new or increased hemorrhage (i.e. edema related) associated with an increase of 4 or more points on the NIHSS or GCS increase  $\geq 2$  persisting for at least 24 hours, and/or requiring emergency surgical decompression or resulting in death.
- Symptomatic Ischemic Stroke: A new ischemic stroke (ipsilateral, contralateral; contiguous with bleed/operative site or remote; cortical, subcortical or perforator distribution) within 90 days associated with an increase of 4 or more points on the NIHSS or GCS increase  $\geq 2$  persisting for at least 24 hours and/or requiring emergency surgical decompression or resulting in death.
- Surgical complications related to Apollo / Artemis MIES: Surgical site infection, brain abscess or confirmed meningitis, or documented complication(s) deemed specifically related to the procedural anesthetic (medication, access or intubation related) within 90 days.

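### The visit procedure in 5.9.1 appears to search and ask only for neurological events, while 5.9.3, 7.5.2, 16 and 16.2 cover all serious adverse events, so non-neurological SAEs after discharge may be under-ascertained

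*Combined protocol and SAP*

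**What the plan says.** Section 5.9.3 sets a broad scope: "All serious adverse events occurring during the 365 days of study participation will be recorded". It also says when the assessment happens: "Adverse events and serious adverse events are critical endpoints and will be assessed as they occur and at the scheduled clinic visits". Its definition has no organ-system limit: "A serious adverse event is one that is fatal or life-threatening, is permanently or substantially disabling, requires or prolongs hospitalization", among other criteria. Sections 16 and 16.2 also require SAEs to be recorded without restriction by type, and 16.2 adds a 24-hour reporting rule. Section 7.5.2.1 sends periodic reports of all AEs and SAEs to the Trial Operating Committee (TOC) and the DSMB.

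Section 5.9.1 describes what is done at each visit. For the record it says: "At each visit, the patient medical record will be surveyed for any new or interim neurological adverse or serious adverse events". For the interview it says: "In addition, the patient or LAR will be asked about any interim neurological adverse or serious adverse events". One further item follows: "The subject or LAR will also be specifically asked about any interim neurosurgical procedures".

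Table 1 has a row headed "Adverse Events", marked from treatment through the one-year visit, with no neurological qualifier.

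**The concern.** The recording requirement and the visit procedure do not have the same scope. If *neurological* governs both nouns in 5.9.1, a site that follows the text searches and asks for neurological SAEs only. A patient admitted elsewhere between visits for a non-neurological illness has had an SAE under 5.9.3, yet no instruction for an attended follow-up visit directs the site to look for it.

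After discharge, the site no longer observes the patient directly, so solicitation at visits is an important way to learn of events treated elsewhere. At stake is the completeness of the all-SAE count that the TOC and DSMB receive. Comparability between sites is also at stake: the protocol allows up to 10 centres, and a centre that asks broadly would record more SAEs than one that follows the narrow wording, with no difference in actual safety.

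**Working it through.** The plan states no figure to reproduce, and no arithmetic applies. The check is a comparison of the relevant sections.

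1. **What must be recorded.** Sections 5.9.3, 16 and 16.2 say all SAEs. None limits them by organ system, and the definition in 5.9.3 includes any event that requires or prolongs hospitalization.

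2. **What is sought at follow-up visits.** Section 5.9.1 is the only text that says what is searched for and asked at attended visits after discharge. Both steps carry the word *neurological*, and the one added item is neurosurgical. Section 5.7.1 does call for an unrestricted adverse event review at discharge, so in-hospital events are less exposed. The gap concerns the later visits.

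3. **How the phrase can be read.**
   - Narrow: neurological AEs and neurological SAEs. The setting favours this, since the same paragraph deals with neurological assessments and neurosurgical procedures.
   - Broad: neurological AEs, plus SAEs of any kind. This would agree with 5.9.3 and 16.
   - If both readings are open, sites can apply different ones, so ascertainment may vary between sites even though neither site departs from the text.

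4. **Whether other routes close the gap.**
   - *Table 1.* The unqualified row fixes when adverse events are assessed. It does not say how, and 5.9.1 is where the how is given.
   - *Assessment as events occur (5.9.3) and the 24-hour rule (16.2).* The 24-hour clock starts when site staff learn of the event. It governs reporting of known events, not the finding of unknown ones.
   - *Missed visits (8.1).* An AE form is required if an SAE caused the absence. A patient who was admitted elsewhere, recovered and then attended is not caught.
   - *Focused exam and concomitant medication review (Table 1).* Either may bring an illness to light, but neither is an SAE inquiry.
   
   Each route captures some events. None prescribes a search or question for non-neurological SAEs at an attended visit.

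5. **Events the protocol itself singles out.** The list for narrative reports in 5.9.3 includes surgical site infection and complications of the procedural anesthetic within 90 days. These need not be neurological, so the narrow wording does not clearly cover everything on that list.

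6. **Direction and size.** Events that are not sought can be missed but not added, so the bias in the all-SAE count is downward. The size would need two inputs: the rate of non-neurological SAEs after discharge and the share that sites learn of without asking. The documents give neither, and any percentage would only return whatever was assumed.

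**The case against.** A reader might infer that non-neurological SAEs after discharge are never looked for and go uncounted. The documents do not support that. Section 5.9.3 is itself a visit-level instruction with no neurological limit, Table 1 repeats it at every visit through one year, 8.1 catches SAEs behind missed visits, and 16.2 obliges sites to report any SAE they learn of in every phase of the study. Possible under-ascertainment is as far as the text goes.

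The strongest counter-argument is that the conflict depends on parsing. Read broadly, the phrase already covers SAEs of any kind and agrees with the rest of the protocol. That reading is defensible, and nothing shows that restricted solicitation was intended. It does not dispose of the point, because a site cannot tell from 5.9.1 which reading applies, and the narrow one is the more natural.

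It is also fair to say that the consequence is limited. The primary endpoints are recruitment and 180-day follow-up. The primary safety outcome in 7.5.1 is death within 90 days, and death is both a listed event for narrative reporting and a category of the mRS. Most of the events singled out for DSMB review are deaths or intracranial events that the narrow wording would still reach. All of this stands. What remains is the all-SAE reporting to the TOC and DSMB under 7.5.2.1.

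**Conclusion.** The inconsistency is real. On its natural reading, the visit procedure in 5.9.1 is narrower than the all-SAE requirement in 5.9.3, 7.5.2, 16 and 16.2. On the most favourable reading it is ambiguous. Non-neurological SAEs after discharge may be under-ascertained, and ascertained differently between sites. The bias in the all-SAE count is downward and of unknown size. The primary endpoints and 90-day all-cause mortality are little affected.

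The conclusion assumes that sites take 5.9.1 as their working instruction at visits, and that some SAEs treated elsewhere would not reach them otherwise. It does not depend on the separate conflict over the SAE recording period (365 days in 5.9.3, 90 days in 16 and 16.2): the 3-month visit is common to both periods, so the gap exists under either. That conflict needs its own reconciliation, because it settles whether SAEs after day 90 are to be recorded at all.

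**What to change.** Reword both sentences in 5.9.1 so that, at every visit, the record survey and the question to the patient or representative cover any serious adverse event of any organ system, explicitly including any hospital admission since last contact. Keep the neurological adverse event and neurosurgical procedure items as additional prompts. This brings 5.9.1 into line with 5.9.3, 7.5.2, 16 and 16.2 and removes the choice between readings.

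If solicitation is meant to be neurological only, say so in 5.9.1 and 5.9.3, and report SAE counts with that limit stated.

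The cost is two sentences and one scripted question at visits that already take place, with no new visit or test. The downside is a few more SAE forms and a slightly less favourable SAE count.
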